4.2.2.3 Demographics and risk factors

Risk factors for severe pneumonia will be collected from each case and control. These data will be used to control for confounding in the case control analysis, to describe the epidemiologic setting of the sites and to inform the global projection models. Furthermore, other putative risk factors for severe pneumonia will be assessed by examining their occurrence among cases compared with controls. The case control analysis for causal inference assumes that controls represent the population from which cases are derived. We will obtain demographic data, information on socio-economic status and access to health care, to assess this assumption. Case and control health care records may be reviewed to obtain some of this data (e.g. immunization history, ARV treatment history, current/previous enrollment in another study, and CD4 counts if HIV-positive).

Table VI. Risk Fa	ctors*		
Category	Risk factor /Variable	Category	Risk factor/Variable
Demographic	Age	Co-morbidities/	Diarrhea
	Sex	intervention	Sickle Cell Disease
	Mortality status of		Prematurity
	Mother/Father		
	Maternal age		Anemia
	Father's education		Antibiotic use
	level		
	Maternal literacy		Steroid treatment
	Race/Ethnicity		Birth weight
Nutrition	Breastfeeding		
	Vitamin A		
	supplementation		
		Family	Rural or urban residence
	Zinc	environment	Number of siblings
	supplementation		
			Type of home
			(compound/single
			family) Sex of siblings
			Sex of siblings
			Age of siblings
	Vitamin D status		Number of children
	(lab test on stored samples)		living under one roof
	Malnutrition: will be assessed by z		Birth order
	score from weight		Number of people in the
	and height;		family
	Pedal edema	1	Temporary guests in the
			household
			Out-of-home care
Vaccination	BCG		
history			Ventilation in the main
	DPT3 Measles	-	living area Smoker in the house
	HiB		Maternal smoking

Table VI. Risk Fact	ors*		
Category	Risk factor /Variable	Category	Risk factor/Variable
	PCV		Urinary cotinine levels in child (lab test)
	Influenza		Child being carried on mother's back while cooking
	Rotavirus		Type of cooking fuel
Co-morbidities/ intervention	Cold/ hypothermia (temp. threshold to be defined)		Type of stove
	Malaria Parasitemia (lab	Socio-economic status	Maternal Education
	test) Bednet ownership		Head of Household occupation
	and use		Household Income
	HIV infection status		Source of water in the house
	AIDS		Types of wall
	ARV treatment		Household possession
			Electricity
			Type of toilet
			Communication devices
	Cotrimoxazole	Access to care	Possession of
	therapy/ prophylaxis		transportation means
	Mother's HIV status during pregnancy		Means of reaching health facility
	Known TB		Distance to study facility
	DOTS/ TB treatment of adult contact		Cost of reaching study facility
	Past medical history: e.g.		Time to reach study facility
	asthma, heart disease, etc		Place of birth (hospital, home)
	Previous Pneumonia		Mode of delivery (vaginal, c-section)
Environmental Exposure	Arsenic Exposure i.e., total urinary arsenic		

Table VI. Risk Factors*							
Category	Risk factor /Variable	Category	Risk factor/Variable				
	concentration						

*Note: Some sites may collect only a subset of these risk factors

4.2.2.4 Chest Radiography

All cases will have a PA or AP chest x-ray. At some sites, lateral chest radiographs will also be obtained depending on local standards of care and feasibility. All radiographs will be digitized for the purpose of standardized readings on-site or off-site depending on the site capacity and for quality assurance /quality control readings off-site.

4.2.2.5 Digital Auscultation

All cases will have a clinical examination to include respiratory lung sounds. In some sites these sounds may be digitally recorded for standardized categorization. PERCH provides a unique opportunity to build a substantial library of breath sound recordings across multiple populations in a standardized manner. Using this large library, it may be possible to develop and validate a framework for describing and classifying breath sounds that would be consistent and reliable across observers, similar to the algorithm for interpreting chest radiographs described in the previous section. Such a framework could be applied in both clinical and research contexts. In addition, these classifications can be linked to clinical, radiologic, and microbiologic findings as part of the etiologic prediction model, or used to develop computer-based algorithms for the automated classification of breath sounds. The recording will be done using a digital stethoscope which looks and functions as a regular stethoscope but allows for recording of the sounds digitally. The audio-files of the sounds will then be reviewed and categorized by standardized auscultation or by computer analysis. The audio-files will be labeled only with study number and no names or initials. The audio files may be 'read' by on-site or off-site readers depending on site capacity and for quality assurance/ quality control.

4.2.3 Follow up

Standardized data on a limited set of clinical signs and symptoms (respiratory rate, oxygen saturation and amount of oxygen requirement) will be collected at admission, at 24 and 48 hrs after admission, and at discharge to allow inferences to be made about the association between disease progression and specific etiologies and to accurately assess severity. Treatment given during the hospitalization period will also be recorded.

4.2.3.1 24-hour/48-hour limited clinical assessment

A clinical assessment will take place at 24 and 48 hours following admission to measure certain important signs and assess response to therapy:

- O2 saturation
- Respiratory rate
- Volume of O2 required/min
- Lower chest wall indrawing

- Pneumonia danger signs
- Changes in treatment regimen(s)

The "day of admission" will be determined by calendar date, i.e., if enrolled after midnight the 24-hour assessment should be performed the following night or the second morning. No study specimens will be collected.

4.2.3.2 Discharge assessment

The following clinical signs will be assessed at discharge:

- O2 saturation
- Respiratory rate

Discharge diagnosis and clinical status will also be evaluated (i.e., whether fully recovered, left against medical advice, died, etc.).

4.2.3.3 Post-discharge follow-up

All patients discharged alive will be followed up 30 days (window 21-90 days) post-admission to assess vital status and to collect a convalescent serum at all sites and a urine specimen at select sites. Ancillary study data or risk factor information will also be collected at this time. CD4 testing will be done on plasma collected from HIV-infected cases in South Africa and Zambia.

4.2.4 Post Mortem Assessment

The identification of organisms (bacterial, viral and fungal) causing pneumonia in children from a variety of different geographical and ethnic backgrounds will necessarily lead to a spectrum of potential etiologies. The introduction of vaccines against two of the commonest causes of severe pneumonia, *Streptococcus pneumoniae* and *Haemophilus influenzae b*, will also alter the prevalence of causative organisms in severe and fatal pneumonia. The PERCH study has been established to determine these different etiologies. Assessment of clinical samples such as upper respiratory tract washings, sputum or blood cultures will be tested with routine microbiology and molecular diagnostic methods as part of the PERCH study.

However, standard clinical and laboratory diagnostics often fail to identify the etiology of pneumonia (1). Furthermore, the low specificity of some tests – such as sputum or nasopharyngeal culture render them hard to interpret. Fatal outcome in severe pneumonia reflects infection and disease in the lower respiratory tract and lung parenchyma. This means that diagnosis of the cause of death (on a background of multiple potential commensal organisms within the upper tract) should be more accurate if a 'predominant' organism can be identified in the diseased lung, by localizing the virus/bacteria/fungi to the site of the lung pathology.

This argues for direct examination of lung tissue. The PERCH study will obtain ante-mortem lung aspirates on patients in four sites (i.e. the Gambia, Bangladesh, Mali and South Africa) but only a minority of cases have peripheral consolidation on chest x-ray amenable to lung aspirate. An alternative approach to examine lung material directly is to perform post-mortem percutaneous lung biopsy in fatal pneumonia cases. Full autopsy is difficult given the cultural and social constraints on post mortem examination in many of the study countries. Immediate post

mortem percutaneous lung biopsy offers a potentially simpler and less invasive approach to obtain lung tissue than full autopsy.

The advantages of directly obtaining tissue samples from post mortem lung include; (i) microbiological testing to compare post-mortem material with premortem samples on the same patient to validate premortem diagnostics (ii) to establish a diagnosis where these are lacking. (iii) to provide a diagnosis in children who arrive at hospital in extremis and die shortly after arrival, before research investigations can be initiated. In these cases a postmortem approach may provide vital etiological information about this group that is of greatest interest for the prevention of pneumonia mortality.

Lung biopsy samples can be examined by microbiological cultures and molecular diagnostics to detect unrecognized infections or additional infective agents. For example, a recent CDC study on Influenza A H1N1 deaths in the US, showed that testing of post-mortem lung tissue using PCR and immunochemistry assays identified many bacterial lung infections missed by standard clinical methods (2). They may also be examined using histology, where characteristic parenchymal changes may indicate the primary organism (such as granulomatous inflammation in TB, viral inclusion bodies or specific bacteria recognized on Gram staining).

There are a number of potential problems with an autopsy approach to diagnosis in fatal pneumonia. The first is sampling error, whereby the section of lung with the pathology is not sampled; this can be minimized by directing the sampling to the affected lobes. Second, in the perimortem and immediate post mortem period there is widespread cellular degradation and breakdown in physiological barriers (such as in the large bowel), associated with leakage of a mixed flora of intestinal bacteria into the bloodstream and contamination of tissues. The value of post mortem microbiological testing in autopsy tissues has been questioned in the light of these potential problems (3). Studies have revealed, in general, that a proportion of post mortem microbiological diagnoses will be uninterpretable due to contamination, and that success may require choosing the appropriate test to identify a suspected pathogen (such as with fungal pathogens or TB) which may not be a first line microbiological test.

However, despite these potential problems, successful autopsy-based studies of pneumonia etiology, utilizing a purely histopathological approach without supporting microbiology, have had value in revealing unsuspected pathogens (4,5) In our view these data argue that relying wholly on premortem samples and those distant to the diseased lung will result in a significant under- or mis-diagnosis of the causative organism. The extra information which could be derived from postmortem lung biopsy samples in fatal pneumonia cases may significantly add to the data available to the study and will provide information of much greater value in assigning causality in pneumonia than that obtained from peripheral specimens such as nasopharyngeal cultures.

4.2.4.1 Validation of antemortem etiologic diagnosis of fatal pneumonia

Data from postmortem evaluation can also help to validate new and existing diagnostic methods implemented in PERCH. One traditional role that post-mortem examinations have played in clinical care is as a quality assurance mechanism to ensure the accuracy of diagnosis made during the care of patients in life. The PERCH project aims to use Bayesian models to estimate

the contribution of major pathogens to pneumonia etiology and evidence from a lung sample that has high specificity (e.g. lung biopsy material) in a minority of patients who die during treatment may be used to validate and extrapolate evidence derived from lower specificity samples (e.g. nasopharyngeal sampling) among the remaining cases who survive.

4.2.4.2 Improved diagnosis of lung conditions contributing to fatal outcome

Several of the possible primary pathogens in this group may produce 'final common pathway appearances' in the lung such as bacterial pneumonias. However evaluation of post-mortem lung tissue will also enhance TB diagnosis, and provide quality assurance for the methods used for antemortem diagnosis. The diagnosis of pulmonary tuberculosis is important, because it may contribute to a fatal outcome, but also challenging, especially in HIV infected children (6,7). Typically, tuberculosis is diagnosed antemortem on the basis of clinical and radiological findings, but these features are often shared with other infections such as PCP and cytomegalovirus pneumonitis, reducing their specificity in diagnosis. Chintu's study demonstrated a high prevalence of pulmonary tuberculosis in both HIV-positive and HIV-negative patients in Zambian patients (4). However in another study of 93 consecutive deaths of HIV-infected children in South Africa, Rennert et al. confirmed the diagnosis of tuberculosis from lung tissue in only 4% of the patients (8). Some 18% of the patients, who had been on empiric treatment for tuberculosis before death, had no postmortem evidence of active disease in the lung. This disparity may have been due to effective treatment or could indicate clinical misdiagnoses because other pathogens, such as cytomegalovirus and P. jiroveci, were found in all suspected tuberculosis cases. Histological evaluation of lung tissue will improve diagnosis, provide quality assurance of antemortem diagnosis and establish the prevelence of tuberculosis in different populations. This would significantly influence guidelines for national vaccination, prevention and control programs.

Post mortem examination may also help identify pathological processes which contribute to a fatal outcome such as diffuse alveolar damage, and facilitate the diagnosis of pneumonia-like conditions which simulate acute pyogenic pneumonia clinically, like such as Lymphoid Interstitial Pneumonia (LIP), malaria, non-infectious pneumonia (e.g. paraffin ingestion), or non-pneumonic etiology (e.g. anemic heart failure).

4.2.4.3 *Identification of Novel Pathogens*

Identification of novel pathogens is one of the objectives of PERCH. With post-mortem evaluations PERCH can describe the histopathology associated with any new pathogenic agents and determine the likelihood of their role in the etiology and pathogenesis of pneumonia. The potential resource of tissue and DNA available for some cases should also improve the chances of characterizing novel pathogens

4.2.4.4 Study Aims

- 1. Detect infections or co-infections missed during antemortem evaluations
- 2. Validate antemortem diagnosis
- 3. Assess the correlation of histopathological patterns of disease with etiology, particularly if novel pathogens are involved.
- 4. Improve diagnosis of pulmonary tuberculosis and pneumonia-like conditions

- 5. Interpret pathology results in conjunction with clinical data, as the lack of such an analysis has been a limitation of previous studies.
- 6. Form a biorepository for future investigations in this field.

The PERCH project is investigating the etiology of childhood pneumonia in seven different countries. PERCH plans to study the clinical course and determine the microbiological causes of pneumonia in children from 1 month to 5 years old. As part of the PERCH study, we will study tissues from the lung in patients who die of pneumonia in six of these study sites (excluding the Gambia), dependent on the outcome of local IRB approval. A full open autopsy is often difficult to perform for a number of reasons, so we plan to use postmortem percutaneous needle biopsies of the lung.

All PERCH cases will be monitored throughout their hospital stay. The parents of any fatal pneumonia case participating in the study will be approached for participation before or after death depending on the site customs, preference, and community acceptability.

4.2.4.5 **Post Mortem Inclusion criteria**

Cases must meet the following inclusion criteria for eligibility to enter into the PERCH lung biopsy study:

- Enrolled in the PERCH study
- Patient dies in hospital
- Not more than 12 hours have elapsed since death
- Parental/guardian consent given for lung biopsy

4.2.4.6 Post Mortem Exclusion criteria

Children that meet any of the following exclusion criteria will be ineligible to enroll in the postmortem needle biopsy study:

- Parents decline consent
- Lung biopsy procedure cannot be performed

4.2.5 Post mortem Study subject evaluation methods

4.2.5.1 Specimen collection

Prior to the biopsy and specimen collection procedures, any available case x-ray should be reviewed with the operator to determine likely site of disease and therefore the appropriate sampling protocol for either lobar or diffuse disease. Obtaining a representative sample of the lung is important. Pneumonia may be localized to one area of the lung or changes spread across patchy or wide areas of the lung.

By using a percutaneous procedure, some anatomical representativeness can be obtained by taking multiple cores from both sides.

- There will be one biopsy entry site on each side one on the left and one on the right. All lobes of the lung can be sampled through one entry site. One entry per side will minimize physical evidence of the procedure on the body (leaving a punctate scar less than 0.5cm in diameter).
- The biopsy site is in the mid-axillary line in the 5th intercostal space

- The biopsy needle will be used to take multiple biopsies from both sides. Passing the needle in different directions will ensure sampling of different lobes.
- An automatic, reusable needle biopsy system will be used, with an 18G detachable biopsy system allowing sampling of 22mm length cores [Omni-RAM (Agoram) system for soft tissue biopsies].

The text below details the sampling strategy:

- Two Biopsy Sites, Bilaterally in all cases (1 left, 1 right) in mid axillary line
- A total of 16 biopsies will be taken. E.g. the biopsy needle will be reinserted through a single puncture site on each side 8 times to collect tissue samples from different lung segments.
- Providing 5 biopsy cores for Histology, 6 cores for Microbiology, 2 for Molecular pathology, 2 for Molecular microbiology, and 1 core for frozen tissue

Protocols for direction of biopsy sampling will be based on any antemortem evidence for localization of disease, for instance from clinical examination of chest X-ray results. The different biopsies will be preserved in separate fixatives according to their intended use:

A: Histology: 10% neutral buffered formalin for standard histology from formalin fixed, paraffin embedded blocks

B: Microbiology: No preservative, rapid transport to microbiology laboratory for

- i) Gram stain, microscopy and standard agar plate culture
 - ii) mRNA extraction for Multiplex PCR
 - iii) TB culture
- C: Molecular Microbiology: TE buffer for subsequent 16s rRNA typing
- D: Molecular Pathology: RNaLater buffer for subsequent mRNA extraction and PCR
- E: Frozen Tissue: For subsequent immunohistochemistry and PCR

As well as allowing routine histology, and comparative microbiology with any antemortem sampleson the same patient, preservation in RNAlater and Frozen tissue have both been validated for DNA/mRNA and microRNA extraction from autopsy tissues and production of microarrays in lung tumours and interstitial lung disease. (9-11).

4.3 Control selection

Controls selected from the community will be enrolled approximately on a 1:1 basis to cases, with a minimum of 25 controls enrolled per month. Parents/guardians of control subjects will be compensated according to the routine practice at each site. Local practices and IRB guidelines will govern the amount and type of compensation; the amount offered will not be so high as to induce someone to participate in the study. Food and transportation reimbursement are examples of the types of compensation that could be provided by the sites. Specific details will be included in site specific appendices. Basic demographic information on eligible children

Version 6.0_15Nov2013

not enrolled, including the reason for not enrolling, will be collected and used to compare enrolled and non-enrolled children.

[figure not shown]
Table VII presents an overview of the control evaluation schedule of activities. Details for each time point are described in sub-section 4.4 below.

Table VII. Overview of Control Study Evaluations							
	Follow-up time point						
Activity	Day screened	Day enrolled*					
Log of assessed children	Х						
Eligibility assessment	Х						
Enrollment/Consenting		Х					
Specimen Collection:							
Blood		Х					
 Nasal and throat swabs 		Х					
Urine		Х					
Demographic, clinical history and risk factor assessment		x					
Limited clinical assessment (i.e. respiratory signs, respiratory rate, neurological signs, rash, temperature)		X					

*May be the same day of screening for children enrolled at home.

Controls will be selected from the community from which the cases came (but not matched by geographic location). Approximately 1 control per case will be enrolled. PERCH sites will recruit a minimum of 25 control patients per month. In months where the number of cases exceeds 25, sites will enroll controls in an additional 1:1: ratio to achieve the same number as cases enrolled that month.

Figure V. Illustration of control selection rates relative to the case enrollment rates

In the two sites with high HIV prevalence (Zambia and South Africa), a separate control enrollment strategy will be deployed in addition to the above strategy to capture a second group of HIV-infected controls for the etiologic analysis (see section 4.4.6).

4.3.1 Strategy of community control selection

There will be two main stages to the control selection strategy – defining a catchment area and selecting eligible control children from within that catchment area. At the first stage in control selection, the catchment population from which cases are drawn will be clearly defined at each site by examining the geographic distribution of existing cases in the hospital(s). The catchment population includes all residents of the geographic catchment areas served by the study hospitals. The catchment area for the PERCH study could be the entire catchment area of the hospital, or a subset of the catchment area where the majority of cases come from. This latter strategy will be employed for logistical reasons so as not to have to enroll controls over a too expansive area, and for statistical reasons so that controls from very distant areas that rarely use the study hospital would not be over-represented in the controls. In some sites (i.e. Kilifi, Gambia and Bangladesh) a demographic surveillance system (DSS) area will be defined as the catchment area for PERCH. In the other 4 sites, existing case admission logbooks and local knowledge of the area will be used to define an appropriate catchment area for PERCH where the majority of severe pneumonia cases reside.

In the next stage of control selection, one of two strategies will be employed. In some sites, all children in the catchment area will already be enumerated. This will apply to areas with DSS sites (i.e. Kilifi, Gambia and Bangladesh) and with comprehensive birth registries (i.e. South Africa and Thailand). In these sites, a simple random sample of children, frequency matched by age, will be selected from the entire catchment area. There will not be matching by geographic location of the cases.

In the sites without individual household enumeration of the catchment area (i.e. Zambia, Mali), the catchment area will be divided into segments, such as villages or census enumeration areas where the approximate population size of these segments is known. Segments will be selected using simple random sampling with a probability proportional to estimated size as needed for the number of controls to be enrolled each month. To select a household in the selected

segment, either an enumerated list of households will be used and simple random sampling employed or the WHO EPI immunization cluster sample survey method will be used (www.who.int/vaccines-documents/document WHO/IVB/04.23). In brief, this is done by choosing a random direction from the center of the segment and walking from that center to the perimeter, enumerating all households on the line of the walk. Then, a starting household from the enumerated list is chosen randomly and visited to verify if an eligible control is available. If not, the next household in a predefined direction (e.g. left or right) is visited, and so on, until an eligible control is enrolled.

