One issue is what to do when selected individuals do not enroll, either by refusal or other reasons. Since replacement with patients not identified to be selected will lead to selection bias, a larger sample size than needed must be approached to cover non-enrollment. Basic demographic information on eligible children not enrolled, including the reason for not enrolling, will be collected and used to compare enrolled and non-enrolled children.

Version 6.0_15Nov2013

There may be cases of severe pneumonia in the community that will not be captured on the case log (e.g. where a child should be admitted to the hospital but is not.) If children present with severe/very severe pneumonia (and are diagnosed as such) there are no circumstances when they would be turned away. But parents may not permit admission either because they cannot afford the care or must return home (and cannot leave the child behind). These patients might represent a segment of the population at the greatest risk of disease and by missing them we are biasing our estimates for the risk factors and possibly the etiologic distribution. As noted, we will try to capture basic demographic information on such children to compare with enrolled children. However, it is likely that this group will be small at most sites, and regardless, the case log will be able to capture cases that should be admitted so we can count them. Our ability to represent the "community" experience of pneumonia is probably limited much more by cases failing to present rather than by failing to be admitted (e.g. at the Kilifi site, approximately 1/3 of children who die do not seek care during their final illness).

Another challenge will be to capture data on the children who die soon after presentation. There might not be time to properly assess and sample them before they die, which would create a potential bias. Case log data should be collected on them as well, and an attempt made to enroll them even after death if it is locally acceptable to collect post mortem specimens (please refer to the post mortem section in 4.2.5).

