4.3.7 Matching and selection/sampling methods

Controls will be frequency matched on age and season to the cases to ensure that neither factor can confound the primary analysis, i.e. – the association between case-status and infection of the nasopharynx with respiratory pathogens.

Age strata for frequency matching to be used are the following: 28 days-5 months, 6-11 months, 12-23 months, 24-59 months. Seasonality matching will be done by month – attempts will be made to enroll the same number of cases and controls by month, with a minimum number of 25 controls per month. All analyses will incorporate stratification of age and season.

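### In Zambia and Mali a control child's chance of selection depends on how many eligible children share the home, and the unstated search rule leaves the resulting bias undetermined

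*Protocol*

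**What the plan says.** Protocol section 4.3.1 uses two kinds of control sampling. Three sites with demographic surveillance and two with birth registries sample children: "In these sites, a simple random sample of children, frequency matched by age, will be selected from the entire catchment area". Zambia and Mali have no enumeration of individual households, so they sample area segments and then households, from a list or by the WHO EPI walk. The starting household is "visited to verify if an eligible control is available. If not, the next household in a predefined direction (e.g. left or right) is visited". Staff continue from home to home in this way "and so on, until an eligible control is enrolled".

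Section 4.3.2 makes any child aged 28 days to 59 months eligible. Section 4.3.7 adds frequency matching for controls: "Age strata for frequency matching to be used are the following: 28 days-5 months, 6-11 months, 12-23 months, 24-59 months". It also stratifies all analyses by age and season.

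Nothing in section 4.3 says whether the household search is for a particular age band, which child is taken when several qualify, or that the number who qualify is recorded.

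Table VI (section 4.2.2.3) lists number and age of siblings, family size and the number of children "living under one roof" as risk factors. Its footnote allows sites to collect only a subset. Cases are sampled as admitted children (section 4.1.3).

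**The concern.** If a search yields one control however many children in the home could fill the slot, a child who shares the home with competitors is less likely to be chosen than a child without them. Cases carry no such penalty. Controls at these two sites then under-represent crowded homes even when crowding has no effect on pneumonia.

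Three results are exposed:

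- **Crowding odds ratios.** Siblings, children in the home and family size are listed risk factors, so the selection variable is close to the exposure itself.
- **Control-based prevalences.** Sections 2.4 and 6.3.3.4 use these to describe the sites, to obtain population attributable risk and to extrapolate globally.
- **Pathogen odds ratios.** If carriage rises with contact with other young children, control carriage is too low. Section 6.3.3.1 drops nasopharyngeal results at an odds ratio of 1.0 or below and reads values above 1 as pointing to a causal link, assuming no bias or confounding.

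The protocol's own standards point the same way. Section 4.2.1 requires, for cases, a known selection probability for every eligible child. Section 4.2.2.3 says causal inference assumes that controls represent the population that gives rise to the cases.

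**Working it through.** The protocol gives no household-size data and no crowding odds ratio, so it has no figure of its own to reproduce on the bias. All household and carriage inputs below are assumptions, shown as ranges.

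**Scope (Table XIV).** Community controls: 900 + 900 + 600 + 800 + 1200 + 1200 + 850 = 6450. Adding 750 HIV-infected controls gives the table's 7200. Mali and Zambia supply 900 + 850 = 1750 (27%) of the community controls and 700 + 800 = 1500 of 6300 cases (24%).

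**Model.** Let c_k be the share of children, and so of cases under the null, in homes with k under-fives. Let π_k be the chance that such a child is the one taken when the home is reached. Control shares are proportional to c_k × π_k. The null odds ratio for k versus 1 is 1/π_k.

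**Any under-five qualifies: π_k = 1/k.**

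- Two versus one: 1/(1/2) = 2.0.
- Any other under-five versus none, for child-level mixes over k = 1 to 4 of 50/50/0/0, 50/40/10/0, 40/40/15/5 and 25/35/25/15: 2.0, 2.14, 2.29 and 2.54.
- Worked case: homes holding 1/2/3 under-fives in 60/30/10%. Mean 1.5 per home; children with another at home 0.9/1.5 = 60%; sampled controls 40%. Odds ratio (0.6/0.4)/(0.4/0.6) = 2.25.

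**Search directed to one age band: π_k = E[1/(1+J)]**, where J is the number of other children in the same band. With independent ages (as in a shared compound), J is binomial(k−1, q) with q = band width/59 months. For k = 2, the odds ratio is 1/(1 − q/2).

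| Band | q | k = 2 | k = 3 | k = 4 |
|---|---|---|---|---|
| 28 d-5 m | 5/59 | 1.04 | 1.09 | 1.14 |
| 6-11 m | 6/59 | 1.05 | 1.11 | 1.17 |
| 12-23 m | 12/59 | 1.11 | 1.23 | 1.36 |
| 24-59 m | 36/59 | 1.44 | 1.95 | 2.50 |

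Section 6.3.1 assumes 50% of cases at 1-11 months, 30% at 12-23 and 20% at 24-59. Splitting the first group evenly over its two bands (an assumption), the geometric mean for k = 2 is about 1.14.

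For two full siblings spaced 18 to 48 months apart, the odds ratio is 1.00 in the three younger bands, since no band of 12 months or less can hold both. At 24-59 months it is 1.21 by simulation.

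**Carriage with no true effect.** Example: carriage 30% without and 50% with another under-five, half of children having one. Cases 0.5 × 0.5 + 0.5 × 0.3 = 0.40. Controls, with one third exposed, 0.367. Odds ratio (0.40/0.60)/(0.367/0.633) = 1.15.

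- Any under-five qualifies, four mixes, carriage 10/20%, 30/50% and 50/70%: 1.15 to 1.20.
- Band-directed: about 1.02 to 1.03 overall, 1.06 to 1.08 in the oldest band.

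**Consequence at the protocol's two-sided alpha of 0.01.** A spurious crowding odds ratio of 2.0 (50% of cases exposed) would be significant at either site with probability near 1. A spurious carriage odds ratio of 1.15 (40% of cases positive) would be significant with probability 11% in Mali and 12% in Zambia, against a nominal 1%.

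**Effect of weights.** Weighting each control by the number of children who competed for its slot returns the null crowding odds ratio to 1.00 under either rule. Weighting a band-directed sample by all under-fives can over-correct. Where the selection odds ratio was 1.00, doubling the weight of two-child homes gives 1/2 = 0.5.

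For the 60/30/10 mix under the any-under-five rule, the Kish design effect is E[k²]/E[k]² = 2.7/1.5² = 1.20.

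**The case against.** The strongest reply is that age matching probably directs the search. Field staff who need a child aged 6-11 months would pass over siblings in other bands. In two-child homes under 24 months, where 80% of cases are expected, the effect then nearly vanishes. This is plausible and rules out presenting about 2 as the expected bias. It does not settle the matter, because section 4.3.1 does not say so and section 4.3.2 read literally admits any under-five.

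One control per household is also inferred from the stopping rule; no cap is written. The walk is described only in outline, with reference to a WHO manual not available here. That stands, and is a reason to write the rule down.

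Weights may appear in an analysis plan that is not shown, so their absence alone is no finding. But choosing the child and counting those eligible happen in the field. An analysis plan can weight only if the count exists, and Table VI does not guarantee it at every site.

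On carriage the reply is largely right. Section 4.2.2.3 commits the risk-factor data to confounding control, and adjustment for the number of competing children removes this bias. Adjustment cannot repair the crowding odds ratio, where that number is essentially the exposure, or the control prevalences.

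Two further faults might be inferred, but neither adds much. "Segments will be selected using simple random sampling with a probability proportional to estimated size" joins two designs, yet a proportional-to-size draw is evidently meant. Section 4.2.1 warns for cases, "Since replacement with patients not identified to be selected will lead to selection bias", but that concerns selected cases who do not enroll. Moving to the next home is mainly screening, and section 4.3 plans to compare eligible children who are not enrolled with those who are.

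**Conclusion.** The point holds in a conditional form. Household selection that stops at one enrolled control makes a child's chance of selection fall with the number of competing children. This affects Zambia and Mali only: 27% of community controls and 24% of cases. Under the assumed household structures, the null crowding odds ratio there is:

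- 1.00 to 1.11 below 24 months in two-child homes, if the search is band-directed (up to 1.36 with four under-fives);
- 1.2 to 1.4 at 24-59 months in two-child homes, if band-directed (1.95 to 2.50 with three or four);
- 2.0 to 2.5 if any under-five qualifies.

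A reader might infer that the design by itself creates an odds ratio of about 2, or that it seriously distorts the pathogen results. The documents support neither. The first needs every under-five at home to compete for one slot, or, under a band-directed search, three or more under-fives at 24-59 months. The second amounts to a factor of about 1.02 to 1.20 in the scenarios tried, before dilution by the other five sites, and can be removed by adjustment. The direction and the missing rule are established; the size is not, because the protocol omits what determines it.

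**What to change.** In section 4.3.1, for Zambia and Mali:

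1. State whether each household search is directed to a matching age band or accepts any eligible child under five.
2. State that one child is chosen at random among those eligible for the slot.
3. Require the number of such children to be recorded at the visit at both sites, outside the optional part of Table VI.
4. Weight each community control at these sites by that number: children within the band if the search is band-directed, all eligible under-fives otherwise. Use the weights for crowding odds ratios and all control-based prevalences. For pathogen contrasts, use the weights or adjust for the same number.

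The rule in step 1 must be settled before any weights are applied, because the wrong count can reverse the bias. If enrollment has taken place, establish what field staff did and reconstruct the count from sibling ages and children in the home where collected.

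The cost is a few sentences, one recorded item and a control design effect of about 1.2 at the two sites if any under-five qualifies. At 1.20, the 1750 controls carry the information of about 1750/1.20 = 1458 in weighted analyses. Under a band-directed search most weights would be 1 below 24 months in two-child homes, and the loss there would be smaller.
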